each service leaving vacancies for 200 new referrals per year across the three sites. We aim to recruit and randomise 60 participants from across the three sites and have allowed 15 months for recruitment. A main aim of the feasibility trial is to establish whether randomisation to different types of supported accommodation is possible, including its acceptability to service users, clinicians and service providers and its feasibility given the complex logistics involved. A relevant comparison here is with the "Individual, Place and Support" model of supported employment. Though originally considered too logistically challenging for evaluation through randomised controlled trials, such trials have now been carried out successfully (Crowther et al., 2001; Twamley et al, 2003; Burns et al., 2008). Similar challenges may apply here. Service users do not necessarily have much control over the type of supported accommodation they are referred to. Clinicians and providers tend to steer the process and may be anxious about a service user's suitability for one of the two types of supported accommodation we propose to compare. This is not a unique problem in that professionals and clinicians often have opinions that are not evidence based about what is best for their patients. However, we will need to engage with key individuals in each region to agree acceptable protocols. Where there is agreement for a participant to be randomised and they have given their informed consent, they will be randomly allocated on an equal basis to either the supported housing service or the floating outreach service. Randomisation will be conducted independently of the research team by a statistician from the Pragmatic Clinical Trials Unit based at Queen Mary's University London. Randomisation will be stratified by site to ensure equal numbers of participants are allocated to both types of service within and across sites.

COMPARISON SERVICES

Supported housing services provide a constant level of staffing on-site to a number of service users living in individual or shared tenancies with the expectation of move-on within two years. Floating outreach services provide support of flexible intensity to service users living in an independent tenancy which is time-unlimited. Current evidence does not suggest that there are major differences in the content of care and support provided by these two supported accommodation models.

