The **content of care delivered by both types of service** will be assessed during the feasibility trial 6 and 12 months after participant randomisation using:

- a) a standardised quality assessment tool completed by the supported accommodation service manager through a face to face interview with the researcher. This tool was developed by the authors and subsequently adapted for supported accommodation services during an earlier phase of this programme of research (QuIRC; Killaspy et al., 2010). Managers will also be asked to complete a proforma to provide descriptive data on the service. We will complete these tools once for each service, 6 months after the first participant is randomised to that service.
- b) a proforma to collect information about the number of contacts made by staff of the supported accommodation service with service users over the previous 3 months. This information will be collected from service users and corroborated with staff and case note review 6 and 12 months after randomisation.
- c) a standardised measure that assesses the amount and complexity of activities service users have engaged in over the previous week (the Time Use Diary, Jolley et al., 2006). This measure will be completed separately by a staff member who knows

the participant well (such as the participant's keyworker) and the participant through face to face interviews with the researcher, 6 and 12 months after randomisation.

OUTCOME ASSESSMENTS

The main aim of this study is to assess the feasibility of a large scale randomised controlled trial assessing two existing models of supported accommodation. We will therefore assess a number of aspects of feasibility: the number of referrals to the trial; the number recruited and randomised; attrition (i.e. the number who withdraw consent to continue with the research, decline to move to the allocated service, or cannot be located at follow-up); and the time from recruitment to moving into either type of supported accommodation. Data on these areas of uncertainty will inform the feasibility of a larger scale trial including the rate at which recruitment could take place and the likely number of sites required. If we are able to recruit our target of 60 participants (who would all be randomised) from three sites over our 15 month recruitment period then we will consider a large scale trial to be feasible.

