We will ask those who are recruited whether they have any preference for either of the two models (and if so, which) at baseline. We will also ask the referring clinician if they have any preference for the type of supported accommodation their client receives as part of the staff baseline interview. We will ask the service user and their care coordinator/keyworker to give their feedback about their experiences of randomisation and views about the trial using a simple proforma which will be included in the 12 month follow-up interviews. In addition, we will ask other key individuals involved in the supported accommodation referral process to give their feedback using the same proforma.

We will ask service users who do not wish to be randomised (and clinicians who do not agree for their service users to participate) their reasons for this. We will invite up to 60 service users in this group to participate in a naturalistic follow-up to determine their outcomes over time. If they are willing, we will collect the same baseline and outcome data as for randomised participants from staff and service users.

Baseline assessment

Before randomisation we will collect data on participants' age, gender, ethnic group, diagnosis, length of contact with mental health services and previous type of accommodation from staff and case notes. We will also assess their social function using the staff rated Life Skills Profile (Parker et al., 1991) and adjust for this in our analyses.

12 month outcome assessment

We will test the feasibility of collecting the following outcomes for service user participants at 12 months follow-up. These outcomes include those suggested by staff and service users in our previous qualitative study and those suggested in the background section of this protocol. Where relevant, assessments will be carried out at baseline as well as 12 month follow-up (denoted by *) in order to assess for baseline scores and adjust for these in our analyses. Where we have more than 30% missing data we will consider that outcome to be unfeasible to include in a larger trial. If there is more than 10% missing data for any outcome (but less than 30%) we will consider if there are ways to improve the response rate.

From service user interviews:

- Mental health (**Brief Psychiatric Rating Scale*** [Overall and Gorham, 1962])
- Quality of Life (**Manchester Short Assessment of Quality of Life*** [Priebe et al., 1999])

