Service use in the period before follow-up will be measured using the CSRI (Beecham and Knapp, 1999) and combined with unit costs. The service costs will be derived from expenditure data. Cost-effectiveness of the two types of service will be assessed by combining service costs with the composite outcomes described above. We will also use the SF36 (Ware et al., 1996) and EQ5D (Williams, 1995) to derive QALYs. The use of both is appropriate because there are concerns about using the EQ5D in this population (McCrone et al., 2009). The SF36 and EQ5D will be collected from service users at baseline and 12-month follow-up.

The relationship between EQ5D and SF36 (via the SF6D) QALYs and the other outcome measures will be examined. Uncertainty around the cost-effectiveness

estimate will be assessed using planes and cost-effectiveness acceptability curves and will depend ultimately on which primary outcome(s) is chosen.

OUTPUTS

Assessment of feasibility, required sample size and appropriate outcomes for a large scale randomised trial of two supported accommodation models.

TIMEFRAME

Month 31-44. Recruitment and baseline data collection

Month 31-40. Qualitative interviews with staff and service users

Month 41-54. Follow-up data gathered 12 months after randomisation

Month 55-60. Data cleaning, analysis and write-up

FINANCE

The Quality and Effectiveness of Supported Tenancies for People with Mental Health Problems (QuEST) Project is funded by the National Institute for Health Research Programme Grants Scheme in the amount of £1,642,079. The award will be administered by Camden and Islington NHS Foundation Trust.

COMPLAINTS

In the event of a complaint about the conduct of the study, the complaints should be reported immediately to the JRO [contact] who decide which complaints policy applies and who will be the lead organisation. The NHS complaints policy can only apply where the research subject is recruited through an NHS Trust. In other circumstances the UCL complaints policy will apply.

INDEMNITY

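### The protocol's timeframe gives 14 months for recruitment where the text says 15, and its 12-month follow-up window closes 2 to 3 months before the last visits fall due

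*Protocol*

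**What the plan says.** Four places in the protocol bear on the calendar.

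- **TIMEFRAME** gives "Month 31-44. Recruitment and baseline data collection", then "Month 41-54. Follow-up data gathered 12 months after randomisation". A final phase for cleaning, analysis and reporting occupies months 55 to 60.
- **ALLOCATION OF PARTICIPANTS TO TRIAL ARMS** sets the target, "We aim to recruit and randomise 60 participants from across the three sites", and says the team "have allowed 15 months for recruitment".
- **OUTCOME ASSESSMENTS** repeats the 15 months inside the feasibility criterion: 60 recruited "from three sites over our 15 month recruitment period then we will consider a large scale trial to be feasible".
- **12 month outcome assessment** fixes the time point: "We will test the feasibility of collecting the following outcomes for service user participants at 12 months follow-up". It also sets two completeness thresholds. Above 30% missing, an outcome is judged unfeasible for a larger trial. The lower threshold begins "If there is more than 10% missing data for any outcome" and, up to 30%, leads the team to consider how response might be improved.

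**The concern.** The timetable disagrees with the text on how long recruitment lasts, and its follow-up line disagrees with itself. If data are gathered a year after randomisation, the follow-up window should lie 12 months after the recruitment window at both ends. It does not.

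If the windows were applied as printed, the latest recruits would either have no 12-month outcome or be seen early, at roughly 9 to 11 months. In a feasibility study, completeness of outcome collection is one of the main results. Gaps produced by the calendar would be counted with gaps produced by participants and staff, and would feed the 10% and 30% thresholds as if they described how collectable each measure is. Case-note outcomes would not escape, because for late recruits the 12-month period would not yet have elapsed when collection closed.

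**Working it through.** **Inputs (all from the protocol).** Recruitment months 31-44, follow-up months 41-54 and final phase months 55-60 (TIMEFRAME); recruitment of 15 months and a target of 60 (ALLOCATION OF PARTICIPANTS TO TRIAL ARMS, OUTCOME ASSESSMENTS); outcome at 12 months (12 month outcome assessment). Uniform accrual is my assumption; the protocol gives no accrual pattern.

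**1. Recruitment length.** Counted inclusively, 44 − 31 + 1 = 14 months. Counted exclusively, 44 − 31 = 13. Neither reproduces 15. Inclusive counting is the timetable's own convention, since its blocks 31-40, 41-54 and 55-60 run on without gaps. Fifteen months from month 31 would end in month 45.

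**2. Offset of follow-up from recruitment.** Start: 41 − 31 = 10 months. End: 54 − 44 = 10 months. Both should be 12.

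**3. When 12-month visits fall due.**

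| | Recruitment 31-44 | Recruitment 31-45 |
|---|---|---|
| First visit due | 31 + 12 = 43 | 31 + 12 = 43 |
| Last visit due | 44 + 12 = 56 | 45 + 12 = 57 |
| Window opens early by | 43 − 41 = 2 months | 43 − 41 = 2 months |
| Window closes early by | 56 − 54 = 2 months | 57 − 54 = 3 months |
| Months left to month 60 | 60 − 56 = 4 | 60 − 57 = 3 |

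**4. Who is affected.** A visit falls inside the window if randomisation month + 12 ≤ 54, that is, month 42 or earlier. Those randomised in months 43-44 (or 43-45) are due after the close. If seen at month 54 instead, they would be at 54 − 43 = 11, 54 − 44 = 10 or 54 − 45 = 9 months.

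**5. Share of 60, by accrual pattern.** For the linear patterns, monthly weights run 1, 2, … up to 14 or 15 (rising) or the reverse (falling).

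| Accrual | 14 months | 15 months |
|---|---|---|
| Uniform | 2/14 = 14.3% (8.6 people) | 3/15 = 20% (12 people) |
| Rising linearly | (13+14)/105 = 26% | (13+14+15)/120 = 35% |
| Falling linearly | (2+1)/105 = 3% | (3+2+1)/120 = 5% |

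**6. Against the protocol's thresholds.** Uniform accrual puts the share above 10% and below 30% in both cases. Front-loaded accrual keeps it under 10%. Of the patterns shown, only 15-month recruitment with rising accrual passes 30%.

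**The case against.** The strongest reply is that this is an error in a short work plan and not in the design. The follow-up line itself names the 12-month time point, and the outcome section fixes it independently. Nothing orders collection to stop at month 54 or permits early assessment, and no database lock date is set. A team meeting the conflict would probably run visits into months 55-57, which the 60-month programme can absorb. Much of this stands: the total duration is adequate, and the harm described arises only if the printed windows are followed. What does not stand is that the text repairs itself. No other section reconciles 14 with 15 months or provides for 12-month collection after month 54.

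Three stronger readings are tempting and are not supported:

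- **That 12-month follow-up cannot be delivered.** It can for everyone randomised by month 42, which is 80% to 86% under uniform accrual (12/15 or 12/14).
- **That the calendar alone would rule outcomes out.** Under uniform accrual the shares reach only the band in which the team considers improving response; they stay below 30%.
- **That the feasibility criterion is being judged on 14 months.** The criterion says "over our 15 month recruitment period" and agrees with the allocation section. The timetable is the outlier. Nor can the chance of reaching 60 in 14 rather than 15 months be derived, because the protocol gives no expected rate of randomisation apart from the target itself.

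**Conclusion.** The point holds as an inconsistency in the stated windows. Recruitment is 14 months in one place and 15 in two. Follow-up is offset by 10 months instead of 12 and closes 2 or 3 months too soon, depending on which recruitment length is meant. These statements are calendar arithmetic and need no assumption beyond counting months inclusively.

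The share of participants affected does rest on an assumption. It is 14% or 20% of 60 with uniform accrual, less if recruitment is front-loaded and more if it is back-loaded. That could alone cross the 10% threshold, before any real attrition. It would not cross the 30% threshold unless accrual were back-loaded or other losses were added.

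This is more than a background slip, because follow-up fieldwork and the start of analysis would be planned from these windows and outcome completeness is among the things the study sets out to measure.

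**What to change.** 1. State one recruitment length in TIMEFRAME, ALLOCATION OF PARTICIPANTS TO TRIAL ARMS and OUTCOME ASSESSMENTS. If 15 months is intended, as two of the three sections say, the timetable should read months 31-45.
2. Reset 12-month follow-up to months 43-57, or to months 43-56 if recruitment is to be 14 months.
3. Start data cleaning on a rolling basis while the last visits are still being made, and lock the database only after those visits have been completed and queried.

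**Cost.** This is a timetable amendment; the target of 60 is unchanged, and so is the feasibility criterion if 15 months is kept. If 14 months is chosen, the period named in that criterion must change to match. The clear period for cleaning, analysis and writing up falls from 6 months (55-60) to 3 months (58-60), or 4 months (57-60) with 14-month recruitment. Rolling cleaning recovers part of that. Researcher time for follow-up visits must also extend to month 56 or 57.
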